## **2. LIST OF ABBREVIATIONS**

ACR	Albumin Creatinine Ratio
ADR	Adverse Drug Reaction
AE	Adverse Event
AESI	Adverse Event of Special Interest
ASAE	Always Serious Adverse Events
ASD	Absolute Standardized Differences
BI	Boehringer Ingelheim
BP	Blood Pressure
CA	Competent Authority
CML	Local Clinical Monitor
CRA	Clinical Research Associate
CRO	Contract Research Organization
CTP	Clinical Trial Protocol
CTR	Clinical Trial Report
DKA	Diabetic Ketoacidosis
DMP	Data Management Plan
eCRF	Electronic Case Report Form
EDC	Electronic Data Capture
eGFR	Estimated Glomerular Filtration Rate
EU	European Union
EU PAS	European Union electronic register of post-authorization studies
EU-QPPV	European Union-Qualified Person for Pharmacovigilance

GCP	Good Clinical Practice
GLUT	Glucose Transporter
GPP	Good Pharmacy Practice
HbA1c	Glucosylated Hemoglobin
HDL-C	High Density Lipoprotein Cholesterol
IC50	Inhibitory Concentration
ICH	International Conference on Harmonisation
IEC	Independent Ethics Committee
IRB	Institutional Review Board

ISF	Investigator Site File
LDL-C	Low Density Lipoprotein Cholesterol
LPVM	Local PV Manager
MAH	Marketing Authorisation Holder Activities
MedDRA	Medical Dictionary for Drug Regulatory Activities
MFDS	The Ministry of Food and Drug Safety
NCE	New Chemical Entity
NIS	Non-Interventional Study
NSADR	Non Serious Adverse Drug Reaction
OPU	Operative Unit
PASS	Post Authorization Safety Studies
SADR	Serious Adverse Drug Reaction
SAE	Serious Adverse Event
SAP	Statistical Analysis Plan
SGLT2	Sodium-dependent Glucose Co-transporter 2
SOP	Standard Operating Procedure
SUSAR	Suspected Unexpected Serious Adverse Reactions
T2DM	Type 2 Diabetes Mellitus
TC	Triglycerides
T-Chol	Total Cholesterol
TCM	Trial Clinical Monitor
TMF	Trial Master File
TMM	Team Member Medicine
UTI	Urinary Tract Infection

### **3. RESPONSIBLE PARTIES**

Boehringer Ingelheim (BI) has appointed a Trial Clinical Monitor (TCM), responsible for coordinating all required activities, in order to

- manage the study in accordance with applicable regulations and internal standard operating procedures (SOPs).
- direct the study team in the preparation, conduct, and reporting of the trial,
- order the materials as needed for the study,
- ensure appropriate training and information of Local Clinical Monitors (CMLs), Clinical Research Associate (CRAs), and Investigators of Korea.

Data Management and Statistical Evaluation will be done by BI according to BI SOPs.

The organization of the study will be done by a Contract Research Organization (CRO) with which the responsibilities and tasks will have been agreed and a written contract filed before initiation of the study. A CML will be appointed responsible for coordinating the activities required in order to manage the study in accordance with applicable regulations and internal SOPs in the countries covered by the respective BI OPU. On-site monitoring will be performed by a CRO appointed by BI.

An Investigator Site File (ISF) containing all relevant study related documentation will be maintained according to local regulations and BI SOPs at each study site. A copy of the ISF documents will also be kept as an electronic Trial Master File (TMF) at BI according to BI SOPs. Documents related to participating physician and other important participants, especially their curricula vitae, will be filed in the TMF.

## 4. ABSTRACT

Name of company: Boehringer Ingelheim Korea			
Name of finished medicinal product: JARDIANCE DUO®			
Name of active ingredient: empagliflozin/metformin			
Protocol date: 18 Aug 2016	Study number: 1276.39	Version/Revision: 3.0	Version/Revision date: 31 Jan 2019
Title of study:	A regulatory requirement non interventional study to monitor the safety and effectiveness of JARDIANCE DUO® (empagliflozin/metformin, 5/500mg, 5/850mg, 5/1000mg, 12.5/500mg, 12.5/850mg, 12.5/1000mg) in Korean patients with type 2 diabetes mellitus		
Rationale and background:	According to the local regulations, when a new chemical entity (NCE) is registered, a regulatory non interventional study (NIS) of an extended period (4 or 6 years) should be conducted. Such rNIS can provide supplementary data to monitor the safety of NCEs in a real-life situation. Data collected in randomized clinical study with strict inclusion/exclusion criteria and rigorous monitoring schemes have limitations.		
Research question and objectives:	To monitor the safety profile and effectiveness of JARDIANCE DUO® (empagliflozin/metformin, 5/500mg, 5/850mg, 5/1000mg, 12.5/500mg, 12.5/850mg, 12.5/1000mg) in Korean patients with type 2 diabetes mellitus in a routine clinical practice setting		
Study design:	Observational prospective, non-interventional, open-label, multi-centre study		
Population:	
Patients diagnosed with type 2 diabetes mellitus in Korea.
 
JARDIANCE DUO® is indicated as an adjunct to diet and exercise to improve glycaemic control in adult patients with type 2 diabetes mellitus who are appropriate to take a combination of empagliflozin and metformin.
 
 
• When the patients never experienced prior treatments and monotherapy would not provide appropriate glycaemic control, or
 
• When metformin monotherapy does not provide adequate glycemic control, or
 
• As add-on therapy to sulphonylurea in patients with insufficient glycemic control despite treatment with metformin in combination with SU, or
 
• As add-on therapy to pioglitazone in patients with insufficient glycemic control despite treatment with metformin in combination with pioglitazone, or
 
• As add-on therapy to linagliptin in patients with insufficient glycemic control despite treatment with metformin in combination with linagliptin
 
		

Name of company: Boehringer Ingelheim Korea			
Name of finished medicinal product: JARDIANCE DUO®			
Name of active ingredient: empagliflozin/metformin			
Protocol date: 18 Aug 2016	Study number: 1276.39	Version/Revision: 3.0	Version/Revision date: 31 Jan 2019

 
As add-on therapy to insulin in patients with insufficient glycemic control despite treatment with insulin in combination with metformin, or
 
As add-on therapy to insulin in combination with sulphonylurea in patients with insufficient glycemic control despite treatment with insulin in combination with metformin plus sulphonylurea, or
 
As replacement therapy of empagliflozin plus metformin (Patients switching from separate tablets of empagliflozin (10 mg or 25 mg total daily dose) and metformin to JARDIANCE DUO® should receive the same daily dose of empagliflozin and metformin already being taken.)
 
			

Inclusion criteria:
 
 
Patients who have started at first time on JARDIANCE DUO® in accordance with the approved label in Korea
 
Age <math>\geq</math> 19 years at enrolment
 
Patients who have signed on the data release consent form
 
 
Exclusion criteria:
 
 
Patients with previous exposure to JARDIANCE DUO®
 
Hypersensitivity to active ingredients empagliflozin and/or metformin or to any of the excipients
 
Moderate (stage 3b) and severe renal failure (<math>\text{CrCl} < 45 \text{ ml/min}</math> or <math>\text{eGFR} < 45 \text{ ml/min}/1.73\text{m}^2</math>)
 
Acute conditions with the potential to alter renal function such as: dehydration, severe infection, cardiovascular collapse (shock), acute myocardial infarction, sepsis
 
Type 1 diabetes, acute or chronic metabolic acidosis, including diabetic ketoacidosis with or without coma, history of a ketoacidosis (type 1 diabetes and diabetic ketoacidosis should be treated with insulin).
 
Congestive heart failure requiring pharmacologic management, in particular those with unstable or acute congestive heart failure
 
Radiologic studies involving the use of intravascular iodinated contrast materials (for example, intravenous urogram, intravenous cholangiography, angiography, and computed tomography (CT)
 
			

Name of company: Boehringer Ingelheim Korea			
Name of finished medicinal product: JARDIANCE DUO®			
Name of active ingredient: empagliflozin/metformin			
Protocol date: 18 Aug 2016	Study number: 1276.39	Version/Revision: 3.0	Version/Revision date: 31 Jan 2019

scans with intravascular contrast materials) - Intravascular administration of iodinated contrast media may lead to acute renal failure and has been associated with lactic acidosis in patients receiving metformin. Therefore, in patients with eGFR > 60ml/min/1.73m^2, JARDIANCE DUO® must be discontinued prior to, or at the time of the test and not be reinstated until 48 hours afterwards, and only after renal function has been re-evaluated and has not deteriorated further. In patients with moderate renal impairment (eGFR 45-60 ml/min/1.73m^2), JARDIANCE DUO® must be discontinued 48 hours before administration of iodinated contrast media and not be reinstated until at least 48 hours afterwards, and only after renal function has been re-evaluated and has not deteriorated further.
 
 
• In patients with severe infections or severe traumatic systemic disorders, JARDIANCE DUO® should be temporarily suspended, and should not be restarted until the patient's oral intake has resumed and renal function has been evaluated as normal.
 
• JARDIANCE DUO® should be temporarily suspended for any surgical procedure (except minor procedures not associated with restricted intake of food and fluids) before 48 hours, and not be reinstated until 48 hours afterwards, after renal function has been evaluated as normal.
 
• Patients with malnutrition, starvation, hypostheniam pituitary or adrenal insufficiency
 
• Impaired hepatic function (since impaired hepatic function has been associated with some cases of lactic acidosis, JARDIANCE DUO® should generally be avoided in patients with clinical or laboratory evidence of hepatic disease), pulmonary infarction, severe respiratory impairment, any condition associated with hypoxemia, excessive alcohol intake, GI disorders such as dehydration, diarrhoea or vomiting
 
• Pregnant women, women who may be pregnant, nursing women
 
• Disease which may cause tissue hypoxia (especially acute disease, or worsening of chronic disease) such as: decompensated heart failure, respiratory failure, recent myocardial infarction, shock
 
• Patients for whom empagliflozin/metformin is contraindicated according local label of JARDIANCE DUO®
 
			

Name of company:	Boehringer Ingelheim Korea				
Name of finished medicinal product:	JARDIANCE DUO®				
Name of active ingredient:	empagliflozin/metformin				
Protocol date: 18 Aug 2016	Study number: 1276.39	Version/Revision: 3.0	Version/Revision date: 31 Jan 2019		
		
 
• Current participation in other clinical trials
 
			
Variables:	
Endpoints of safety All reported adverse events in patients who take at least one dose of JARDIANCE DUO® will be noted.
 
Endpoints of effectiveness Change from baseline in HbA1c,
 
[REDACTED]
 
[REDACTED]
				
Data sources:	Field study with new data collection				
Study size:	
Single arm (N=600 approximately)
 
A total of 600 patients will be entered in this study, and each patient will be followed for total three times (baseline, short term 12 weeks follow up, long term 24 weeks follow up). Since T2DM is chronic disease it might be restrictive to collect safety and effectiveness data in short-term (12weeks) period, all patients will be enrolled for long-term (24weeks) surveillance.
				
Study sites:	A total of 600 patients will be enrolled at approximately 20 sites by as many as 20 or more NIS physicians. To minimize the selection bias at the site level, the goal is to have participating centers reflect a balance between general hospitals and clinics for surveillance. The treating physicians will mainly be internists. To minimize the selection bias, consecutive patients from each site who meet inclusion criteria will be enrolled in this study.				
Data analysis:	
1) Analysis of demographic data: Demographic data and the health status of subjects for the safety evaluation will be analysed descriptively. For continuous data, mean, standard deviation, minimum value, and maximum value will be described, while for categorical data, frequency will be shown.
 
2) Safety analysis : In the safety assessment population, the number of subjects to whom AE occurred and the number of AEs will be calculated. Also, the incidence proportion of AEs will be estimated with its 95% confidence interval.
 
3) Effectiveness analysis: Mean, standard deviation, minimum value, maximum value, and median of changes in glycosylated hemoglobin(HbA1c)
 
[REDACTED]
				

Name of company: Boehringer Ingelheim Korea			
Name of finished medicinal product: JARDIANCE DUO®			
Name of active ingredient: empagliflozin/metformin			
Protocol date: 18 Aug 2016	Study number: 1276.39	Version/Revision: 3.0	Version/Revision date: 31 Jan 2019
Milestones: Study duration: MFDS set JARDIANCE DUO® re-examination period from 21 January 2016 to 11 August 2020. The study period is granted as the remaining period of JARDIANCE® (empagliflozin) according to the Standards for Re-examination of New Drugs.			

## 4.1 FLOW CHART

Data points	Baseline	Follow-up 1	Follow-up 2
Visit Number	1	2	3
Week/s	0	12	24
Informed consent	X		
Diagnosis	X		
Inclusion / exclusion criteria	X		
Demographics	X		
Family history of T2DM	X		
Diabetes mellitus complications	X		
Medical history	X		
Physical examination	X	X	X
Anti-hyperglycemic agents	X	X	X
Concomitant medications	X	X	X
JARDIANCE DUO® administration status	X	X	X
Renal function	X A	X A	X A
Effectiveness endpoints	X	X	X
[REDACTED]			[REDACTED]
Changes in lab tests		X A	X A
Adverse events		X	X
Study completion		X	X

A : If available

**5. MILESTONES**

Milestone	Planned Date
Start of data collection	30 Jan 2018
End of data collection	11 Aug 2020
Interim report 1	11 Oct 2017
Interim report 2	11 Oct 2018
Interim report 3	11 Oct 2019
Registration in the EU PAS register	TBD
Final report of study results:	11 Nov 2020

## 6. RATIONALE AND BACKGROUND

### 6.1 RATIONALE

According to the local regulations, when a new chemical entity (NCE) is registered, a regulatory non interventional study (rNIS) of an extended period (4 or 6 years) should be conducted. Such rNIS can provide supplementary data to monitor the safety of NCEs in a real-life situation. Data collected in randomized clinical study with strict inclusion/exclusion criteria and rigorous monitoring schemes have limitations.

This is an observational prospective, non-interventional, open-label, multi-centre national study. It will provide additional safety information of JARDIANCE DUO® (empagliflozin/metformin) in Korean patients with type 2 diabetes mellitus in a routine clinical practice setting.

### 6.2 BACKGROUND

Diabetes mellitus is an increasingly prevalent disease. Recent estimates suggest that the number of people worldwide with diabetes is currently 382 million and is expected to reach at least 592 million within the next 25 years [[R14-1408](#)]. The most common form is type 2 diabetes, which is characterized by insulin resistance, impaired insulin secretion, and increased blood glucose levels. Type 2 diabetes is also associated with microvascular complications [[R09-6405](#), [R09-6406](#)] and elevated cardiovascular risks [[R12-2906](#)].

Diabetes and its complications have become a major cause of morbidity and mortality in Korea. Although diabetes-related mortality has recently decreased from 25.1 per 100,000 persons in 2002 to 19.6 per 100,000 persons in 2009, diabetes is still the fifth-leading cause of death in Korea. Diabetic complications such as renal failure, neuropathy, retinopathy, coronary and cerebral artery diseases, and amputations are associated with increased medical costs and reduced life expectancy. [[R13-1653](#)]

The number of patients with T2DM is expected to increase dramatically from about 3.2 million in 2011 (8.8% of the national population) to about 4.25 million (11.1%) by 2030 [[R12-1019](#)].

Treatment of type 2 diabetes usually involves lifestyle interventions, such as diet and exercise, as well as the administration of antidiabetic drugs. Although initially effective, currently available oral antidiabetic agents often fail to maintain long-term glycemic control or are associated with side effects that may limit their use. Hence, there is an ongoing need for new therapeutic options to provide sustained improvements in glycemic control.

[\[c03606501-02\]](#)

The benefits of empagliflozin in combination with metformin have been shown in 3 main studies in patients with T2DM not adequately controlled by metformin, alone or combined with other antidiabetic agents (pioglitazone or SU). The main measure of effectiveness was the change in HbA1c after 24 weeks of treatment [[s00039827-01](#)].

The studies showed a clinically relevant reduction in HbA1c with empagliflozin compared

with placebo, both on metformin background. Similar benefits were seen in the studies regardless of the other antidiabetic agent being taken.

In addition, the results indicated that treatment empagliflozin on top of metformin background was associated with a decrease in body weight and blood pressure. The combination of empagliflozin and metformin also showed a clinically meaningful efficacy profile in treatment-naïve patients with T2DM.

Supportive evidence was provided from several further studies. Some of these were continuations of the main studies that showed the benefits of empagliflozin and metformin continued with longer therapy [[s00039827-01](#)].

Data for cardiovascular safety of empagliflozin from the EMPA REG OUTCOME® study 1245.25 [c02695839-01] showed that with regard to cardiovascular endpoints, treatment with empagliflozin significantly reduced the risk for the combined endpoint of CV death, MI, or stroke compared to placebo in patients with T2DM and high CV risk on standard of care treatment. Further, empagliflozin significantly reduced overall mortality, heart failure requiring hospitalisation, and the combined endpoint of heart failure requiring hospitalisation or CV death, compared to placebo; and significantly reduced the risk for the combined nephropathy endpoints. The effects on CV outcomes in the subgroup of patients who were on metformin treatment at baseline were consistent with the overall population [[s00039827-01](#)].

Thus, the clinical development programme for the FDC empagliflozin plus metformin has demonstrated the efficacy of empagliflozin in the establishment and maintenance of glycaemic control with additional beneficial effects of reducing weight and blood pressure in patients with T2DM [[s00039827-01](#)].

For a detailed description of the drug profile refer to the local prescribing information of JARDIANCE DUO®.

**7. RESEARCH QUESTION AND OBJECTIVES****7.1 PRIMARY OBJECTIVE**

The primary objective of this study is to monitor the safety profile of JARDIANCE DUO® in Korean patient with type 2 diabetes mellitus (T2DM) in a routine clinical setting.

**7.2 SECONDARY OBJECTIVE**

The secondary objective of this study is to monitor the effectiveness of JARDIANCE DUO® by evaluation of the change from baseline after 12 weeks and/or 24 weeks in the glycosylated hemoglobin (HbA1c), [REDACTED]

[REDACTED] in Korean T2DM patients.

## 8. RESEARCH METHODS

This rNIS is an observational prospective, non-interventional, open-label, multi-centre national study. As per regulation, the re-examination period extends from 21 January 2016 until 11 August 2020. However, active enrolment is to be initiated in 2018 after finalizing the re-imbursement agreement with the authority. The last patient follow up is expected in Aug 2020 and the final report of study results will be submitted to MFDS in Nov 2020. Before initiation of the study, any newly reported adverse events collected from other sources such as spontaneous cases, literature cases etc. will be closely monitored.

This study will be carried out in the manner of successive survey that the investigator will be asked to successively write in the case report forms (CRFs) from the subject who was initially administered the drug following the study start date to the requested number of subjects without omission. Prior to initiation of the study, a written contract shall be concluded, and this contract shall be executed among BI OPU, CRO with the head of the site or the investigator with his/her consent.

Patients will be managed according to the local practice guidelines. The choice of treatment will be solely at the discretion of the participating physician. JARDIANCE DUO® will be administered according to the approved label in Korea. Hence there are no additional risks to patients by participating in this rNIS.

### 8.1 STUDY DESIGN

This is a single arm study with JARDIANCE DUO®.

JARDIANCE DUO® will be prescribed according to the local label and at the discretion of the treating physician. Since this is a non-interventional study, the drug will not be supplied by the sponsor. Furthermore, the sponsor will not cover the expenses related to other medications taken by the patient, interventions, procedures, or diagnostic test.

#### 8.1.1 Method of assigning patients to treatment groups

The choice of treatment is fully at the discretion of the physician and the patient. There is no treatment assignment by a third party.

#### 8.1.2 Dosage and Administration

The recommended dose is one tablet twice daily. The dosage should be individualised on the basis of the patient's current regimen, effectiveness, and tolerability while not exceeding the maximum recommended daily dose of 25 mg of empagliflozin and 2000 mg of metformin.

- In patients not adequately controlled on metformin alone or in combination with other products, including insulin, the recommended starting dose of JARDIANCE DUO® should provide empagliflozin 5 mg twice daily (10 mg total daily dose) and the dose of metformin similar to the dose already being taken. In patients tolerating a total daily dose of empagliflozin 10 mg and requiring additional glycaemic control, the dose can be increased to a total daily dose of empagliflozin 25 mg.

- Patients switching from separate tablets of empagliflozin (10 mg or 25 mg total daily dose) and metformin to JARDIANCE DUO® should receive the same daily dose of empagliflozin and metformin already being taken.

When JARDIANCE DUO® is used in combination with a sulphonylurea and/or insulin, a lower dose of sulphonylurea and/or insulin may be required to reduce the risk of hypoglycaemia (see section on 4. Adverse Events and 6. Interactions on the [13.4 Korean label](#)).

JARDIANCE DUO® should be given with meals to reduce the gastrointestinal undesirable effects associated with metformin.

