## 8.7 DATA ANALYSIS

### 8.7.1 Analysis of demographic data

Demographic data and the health status of subjects for the safety evaluation will be analysed descriptively. For continuous data, mean, standard deviation, minimum value, and maximum value will be described, while for categorical data, frequency will be shown.

Parameters corresponding to demographic data are as mentioned below.

- ① Basic information and disease information
  - Age, gender, pregnancy, body weight, smoking status, diabetes mellitus complications, other medical history, disease period, Family history of T2DM, elderly (Age  $\geq$  65 years), renal impairment and hepatic impairment, allergy, long term use (over 24 weeks)
- ② Medication information
  - Concomitant medication, study drug administration status (total period of drug use, average of daily dose), reason for early interruption, any anti-diabetic agents

To assess the extent of preferential prescribing and the potential for channeling bias, data from the TRAJENTA DUO® (linagliptin/metformin) rPMS will be used as a comparator. The baseline characteristics of patients starting JARDIANCE DUO® for the first time will be compared to the baseline characteristics of patients who started TRAJENTA DUO® for the first time. Proportions and means (SD) of the baseline characteristics will be compared using absolute standardized differences (ASD), where an ASD of at least 10% will be considered a meaningful difference. p-values will also be calculated.

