### 8.7.2 Safety analysis

- ① Among the subjects of safety evaluation, the number of subjects with adverse event incurred and the number of adverse events incurred should be calculated, and the incidence rate of adverse events and the 95% confidence interval should be presented.
- ② The number and percentage of adverse events by type and category should be presented.

- ③ Analysis should be made using Chi-square test or Fisher's Exact test on the adverse event onset status by demographic data of subjects of safety evaluation.
- ④ To estimate any factors that are thought to influence the analyzed incidence rate of adverse events, logistic regression analysis should be conducted, and for statistically significant parameters, the meaning should be described.

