## BOEHRINGER-INGELHEIM PRODUCT

## Indication

Name of BI studied medication or BI product given for the disease in scope of NIS :		
Formulation		
Total daily dose at onset of event (dose, unit)		
Route		
Start date		
Start time		
Date of last administration prior to event		
End date		
End time		
Was the administration correct?	 Yes  No	
If the administration was not correct, check all applicable boxes: overdose, abuse, misuse, medication error, other (i.e. occupational exposure, lack of effect, unexpected benefit)		
 Misuse / Abuse  Medication error  Overdose  Other:		
Action taken with BI studied medication or BI product administered for the disease in scope of NIS as a result of the event (check one)	Dose not changed	
	Dose reduced	
	Dose increased	
	Drug withdrawn	

**Non-Interventional  
Study (NIS) Adverse  
Event Form**

BI Study No: 1276.39	Country:
Site No:	Subject No:

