7.1 Derivation

The items that need to be calculated in this study are as follows, but the following matters may be considered.

- If an additional calculated variable related to the variables defined below is required during statistical analysis, SAP may not be revised, but the variable will be specified in TLFs.
- Depending on the data actually collected, the item units defined in SAP may change (Ex. duration of disease: months → years)

Age

- If the birthday has passed from the date of signing the consent form: (Year of signing the consent form – Year of birth)
- If the birthday has not passed since the date of signing the consent form: (Year of signing consent – Year of birth – 1)

Duration of disease (days)

- (Start date of initial dose of this drug – Date of diagnosis + 1)
- For continuous analysis, if the date is not complete, it is excluded from the analysis.
- For categorical analysis, if the diagnosis date is partially collected, it is analyzed according to the following rules.
 - If 'day' of the diagnosis date is missing: (Year & month of the start date of initial dose of this drug – Year & month of diagnosis date)
 - If there is only 'year' in the diagnosis date: (Year of the start date of initial dose of this drug – Year of the diagnosis date)

Total administration period of this drug (days)

- $\sum_{i=1}^n [(End\ date\ of\ drug)_i - (Start\ date\ of\ drug)_i + 1]$,
i: The i^{th} administration period of the subject in the n times of administration period of this drug
- If the end date of the i^{th} dose is "in progress" or is missing, other than the end date of the last dose:
 - [(one day before start date of $i+1^{th}$ dose) – (dose start date) + 1]
- If the end date of the last dose is 'in progress' or missing, it is substituted in the following order.
 - [(Date of Last visit) – (Start date of drug) + 1]
 - [(Start date of drug) – (Start date of drug) + 1]

Total dose of this drug (empagliflozin/metformin)(mg)

- $\sum_{i=1}^n [(End\ date\ of\ drug)_i - (Start\ date\ of\ drug)_i + 1] * Daily\ dose$
i: The i^{th} administration dose of the subject in the n times of administration dose of this drug

Average of daily dose drug (empagliflozin/metformin)(mg/day)

- Total dose(mg) / Total administration period (days)

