7.2 Categorization

The categories for each item for categorical analysis are as follows. However, categories defined for categorical analysis of continuous data may be added or changed according to the distribution of the actually collected data.

Items	Category
• Children	< 19 years, ≥ 19 years
• Elderly	< 65 years, ≥ 65 years
• Pregnancy	Yes, No, Not Applicable
• Renal impairment	Yes, No
• Hepatic impairment	Yes, No
• Long-term follow-up	< 24 weeks,

Items	Category
	≥ 24 weeks
• Age	19 years ~ 29 years, 30 years ~ 39 years, 40 years ~ 49 years, 50 years ~ 59 years, ≥ 60 years
• Gender	Male, Female
• Smoking status	Never smoked, Ex-smoker, Currently smokes
• Family history of T2DM	Yes, No
• Disease period	< 1 year, 1 year ~ < 5 years, 5 years ~ < 10 years, ≥ 10 years
• Diabetes mellitus complications	Retinopathy, Neuropathy, Nephropathy, Vasculopathy, Etc.
• Medical history	Yes, No
• Allergy	Yes, No
• Renal failure	Yes, No
• Total administration period of JardianceDuo	< 12 weeks, 12 weeks ~ ≥ 24 weeks, ≥ 24 weeks
• Average of daily dose (Empagliflozin)	< 10 mg, 10 mg ~ ≥ 25 mg, ≥ 25 mg
• Average of daily dose (Metformin)	< 1,000 mg, 1,000 mg ~ ≥ 1,700 mg, 1,700 mg ~ ≥ 2,000 mg, ≥ 2,000 mg
• Other anti-diabetic agent	Yes, No
• Concomitant medications	Yes, No
• Discontinuation of study medication	Yes, No
• Severity	Mild, Moderate, Severe
• Serious AE	Yes, No
• SAE Category	Results in death, Immediately life-threatening, Persistent or significant disability/ incapacity, Requires patient hospitalization, Prolongs patient hospitalization, Congenital anomaly/ birth defect, Other comparable medical criteria
• Action taken	Continue, Reduced, Discontinued, Increased, discontinued and reintroduced, Unknown, Not applicable
• Recurrence according to reintroduced	Recurrence, No-recurrence, Unknown,

Items	Category
	Not applicable
• Causality	Certain, Probable/Likely, Possible, Unlikely, Conditional / Unclassified, Unassessable / Unclassifiable
• Factors other than JARDIANCE DUO	None, Concomitant medication, Concomitant diagnoses, Other
• Outcome	Recovered, Not yet recovered, Sequelae, Fatal, Unknown
• Therapy for the event	Yes, No
• Effectiveness	Effectiveness, Ineffectiveness

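### Classing patients by whole-period average empagliflozin dose puts every patient titrated from 10 to 25 mg/day below the top dose class, which dilutes any AE-by-dose comparison

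*Protocol*

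**What the plan says.** **Dosing.** Under Protocol 8.1.2, the recommended start for patients not controlled on metformin "should provide empagliflozin 5 mg twice daily (10 mg total daily dose"). The section continues: "In patients tolerating a total daily dose of empagliflozin 10 mg and requiring additional glycaemic control, the dose can be increased", to 25 mg per day. The same section caps empagliflozin at 25 mg per day. Patients moving over from separate tablets keep their existing daily dose, which may be 10 or 25 mg.

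**Dose metric.** SAP 7.1 defines average daily dose as "Total dose(mg) / Total administration period (days"). SAP 7.2 cuts it into "< 10 mg, 10 mg ~ ≥ 25 mg, ≥ 25 mg". The middle label overlaps the top one as printed; I read it as 10 to below 25.

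**Use in AE tests.** Protocol 8.7.1 lists "study drug administration status (total period of drug use, average of daily dose") among the parameters it calls demographic data. Protocol 8.7.2 item 3 plans chi-square or Fisher tests "on the adverse event onset status by demographic data of subjects of safety evaluation", and item 4 plans logistic regression on factors thought to influence AE incidence. SAP 5.5 uses patients, not patient-time, as the denominator in each category.

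**Data available.** Visits 2 and 3 record dose changes with dates. AE onset dates are recorded, and dose reduction is one of the listed actions taken for an AE. The NIS AE form also asks for "Total daily dose at onset of event (dose, unit").

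**The concern.** The row for 25 mg or more will be read as the safety of 25 mg. By construction it leaves out every patient who reached 25 mg by titration within the study. Under 8.1.2 the only stated route to a 25 mg start is a switch from separate tablets, so the row holds mainly patients already established on that dose. (No start dose is given for treatment-naive patients, so some of them may join.)

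AEs that occur on 25 mg after titration are credited to the lower class, together with all the 25 mg patient-time behind them. In addition, a patient whose dose is cut from 25 mg because of an AE then averages below 25, so the outcome itself decides the class. Safety is the primary objective, and neither document, in the text available, plans an AE analysis by the dose in force.

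**Working it through.** The plan has no figure of its own to reproduce: 600 is a regulatory requirement with no statistical inputs. Step 1 is exact. Steps 2 to 5 use assumed inputs.

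**1. Average dose after titration.** For titration on day d of 168 days, average = [10(d − 1) + 25(169 − d)]/168 = 25 − 15(d − 1)/168. This is below 25 for every d of 2 or more.

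| Titration day | Average, mg/day |
|---|---|
| 2 | 24.91 |
| 15 | 23.75 |
| 29 | 22.50 |
| 85 (after 12 weeks) | 17.50 |
| 168 | 10.09 |

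Correcting the printed class limits does not change this.

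**2. Share of 25 mg time placed in the lower class.** Assume 480 starters at 10 mg, 60 switchers at 25 mg, and a fraction f of starters titrated at week 12. Share = 480f × 12/(480f × 12 + 60 × 24). For f = 10%, 30% and 40% this is 576/2,016 = 29%, 1,728/3,168 = 55% and 2,304/3,744 = 62%.

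**3. Effect on the class ratio (same cohort).** Assume an AE hazard of 0.005 per week at 10 mg, a multiplier of 1.5 at 25 mg, and 30% of starters titrated at week 12, all from those AE-free by then. The top class has 1 − exp(−24 × 0.0075) = 16.5%.
- *No early excess, none titrated:* lower class 1 − exp(−0.12) = 11.3%, ratio 1.46.
- *No early excess, 30% titrated:* 5.82% by week 12, then 0.30 × 8.61% + 0.6418 × 5.82%, total 12.1%, ratio 1.36.

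Now let starters have a higher hazard in weeks 0–12:

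| Early hazard in starters | Ratio, none titrated | Ratio, 30% titrated |
|---|---|---|
| no excess | 1.46 | 1.36 |
| 2-fold | 1.00 | 0.95 |
| 3-fold | 0.77 (16.5/21.3) | 0.74 (16.5/22.2) |

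The low ratios are almost fully present with nobody titrated. They come from comparing new starters with established users, not from averaging.

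**4. Dose reduction after an AE (a separate assumed cohort).** Take 400 patients at 10 mg with 10% risk and 200 at 25 mg with twice the hazard: 1 − 0.9² = 19%, or 38 cases, true ratio 1.90. If half of these cases are dose-reduced, 19 move down. The top class becomes 19/181 = 10.5% and the lower class 59/419 = 14.1%, ratio 0.75. If a quarter are reduced, the ratio is 15.0/12.1 = 1.24.

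**5. Do the obvious alternatives repair it?** Return to the step 3 example with the 3-fold early hazard and a true ratio of 1.5.
- *First-prescribed dose, all patients pooled:* titrated starters began at 10 mg and switchers at 25 mg, so the groups are the same as the SAP classes and the ratio is again 0.74.
- *Crude rates by dose in force, starters only:* at 25 mg, 0.0075 per week. At 10 mg, events per starter are 0.1647 + 0.0312 = 0.1959 over 10.98 + 6.23 = 17.21 weeks, a rate of 0.0114. The ratio is 0.66.
- *The same rates after week 12 only:* 0.0075/0.005 = 1.5, the true value.

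Splitting by time since start is therefore necessary.

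**The case against.** **Reversal.** A reader might infer that the averaging rule can by itself make 25 mg look safer than 10 mg. The documents do not support that. With equal follow-up and a hazard that depends only on dose, misclassing titrated patients pulls the ratio towards 1 and no further. A ratio below 1 needs something more: dose reduction after AEs, which the classing rule does turn into bias, or a difference between starters and established users, which exists without any averaging. Shorter follow-up in the top class could add to it, because denominators are patients. This objection stands.

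**Is the test really planned?** SAP 6.8 refers to a section 6.8.3 that is not in the available text. SAP 5.5 speaks of demographic and baseline factors, and SAP 6 lists treatment status apart from demographics. The AE-by-average-dose test is therefore traced through Protocol 8.7.1 and 8.7.2. That reading is direct, but whether the SAP carries it out cannot be confirmed.

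**Relevance.** This is one non-randomised arm with no dose-response objective, and physicians choose the dose on effectiveness and tolerability. Any dose comparison is confounded. That limits what the comparison can show, but it does not justify a row that omits titrated patients.

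**Flexible categories.** SAP 7.2 allows categories to change with the data. New cut-points would still be applied to a whole-period average, which cannot show the dose at onset.

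**Assumed sizes.** The step 3 cohort covers 540 of 600 patients. Adding 60 switchers at 10 mg moves the 30%-titrated ratios of 0.74 and 0.95 to 0.79 and 0.99. Section 8.1.2 is not itself at fault; it only supplies the titration rule.

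**Conclusion.** The point holds as a misclassification that dilutes. That titrated patients always fall outside the top class is arithmetic and needs no assumption beyond SAP 7.1, SAP 7.2 and Protocol 8.1.2. The dilution from titration alone is modest in the example, 1.46 to 1.36 with 30% titrated at week 12, and it grows with earlier or more frequent titration. Class change caused by AE-driven dose reduction is the more serious route, because it can carry the ratio below 1, but how often it would happen is unknown. The ratios of 0.77 and 0.74 should not be cited as the effect of averaging. All sizes depend on assumed titration shares, AE hazards, dose effects and group sizes, none of which the documents give.

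**What to change.** In SAP 7.1/7.2 and Protocol 8.7.1/8.7.2, keep average daily dose as a descriptive exposure summary and remove it as a factor in the AE tests and the logistic regression.

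In SAP 6.8, add a table of AE counts and patient-time by the empagliflozin daily dose in force at AE onset, as rates with 95% confidence intervals. Show it separately for new starters and for patients who switched from separate tablets, and split it into weeks 0–12 and after week 12. Without the time split, rates among starters remain confounded by early AEs.

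If a patient-level test is wanted, use the first-prescribed dose within the starter and switcher strata, and describe the result as non-causal.

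The cost is one more table, some programming and sparse cells in places. Dated dose changes, AE onset dates and prior antidiabetic drugs are already collected, so no new data are needed. No dosing rule is changed.
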